### 7.2.1 Primary Efficacy Variable

The primary efficacy variable is the change from baseline posttreatment in the daily average frequency of daytime urinary incontinence episodes (daytime is defined as the time between waking up to start the day and going to bed to sleep for the night). The daily average frequency of daytime urinary incontinence episodes is obtained using the total number of daytime urinary incontinence episodes recorded in a 2-day bladder diary divided by 2, and baseline frequency is defined as the daily average frequency of episodes of daytime urinary incontinence preceding the study treatment. Each daytime period recorded in the bladder diary is normalized to represent a 12-hour period to account for differing durations of the daytime period. The daily average frequency of daytime urinary incontinence episodes will be adjusted by the normalized daytime period.

The primary timepoint will be week 6 posttreatment.

For the baseline and posttreatment data, a patient must have at least 1 valid diary day (defined as a day where there is 1 or more urinary episodes [eg, incontinence, catheterization, or voluntary void] during the daytime collection period [between waking to start the day and going to bed to sleep at night]). In the case of patients who partially complete their diary, providing that at least 1 valid diary day out of 2 is available, the 2-day frequency of daytime urinary incontinence will be prorated with the value from the valid diary day.

If less than 1 diary day out of 2 has been completed, then the frequency of daytime urinary incontinence will be considered as missing. Missing frequency of episodes of daytime urinary incontinence at baseline will be imputed using the median of all nonmissing values at baseline within the same treatment group. For the scheduled visits up to week 6 after the study treatment, missing frequencies of episodes of daytime urinary incontinence will be replaced using the last observation carried forward approach. No imputation will be done for missing values on visits after the week 6 visit.

### 7.2.2 Secondary Efficacy Variables

There are 7 secondary efficacy variables assessed at the week 6 primary timepoint:

- change from baseline in MCC (mL)
- presence or absence of an IDC
- if an IDC is present, change from baseline in  $P_{det,Max1stIDC}$  (cm H2O)
- change from baseline in  $P_{det,Max}$  (cm H2O)

- change from baseline in DLPP (cm H2O)
- change from baseline in average urine volume at first morning catheterization (mL)
- presence or absence on night time urinary incontinence

No imputation will be done for the missing values of the secondary efficacy variables. For the urodynamic secondary variables (MCC, presence/absence of an IDC, PdetMax1stIDC, PdetMax, and DLPP), the values provided by the central reviewer will be used.

The average urine volume at first morning catheterization will be calculated from the values recorded in the bladder diary. Similarly the presence/absence of night time urinary incontinence will be based on the response to the question asked each morning in the diary as to whether the patient had urinary incontinence during the night.

## 7.3 Hypothesis and Methods of Analysis

All data will be summarized with descriptive statistics and/or frequency tables. Categorical variables will be analyzed using Fisher's exact test, Pearson's chi-squared test, or Cochran-Mantel-Haenszel (CMH) methods, as appropriate. Continuous variables will be analyzed using analysis of variance (ANOVA) or analysis of covariance (ANCOVA), as appropriate. For the evaluation of efficacy analysis described below, a 2-sided test with a p-value  $\leq 0.05$ , unadjusted for multiplicity, will be considered statistically significant, unless specified otherwise.

### 7.3.1 Primary Efficacy Analyses

The primary efficacy analysis will be based on the mITT population, with imputation of missing values as described in Section 7.2.1. The primary timepoint will be week 6 after treatment.

For each of the BOTOX doses, descriptive statistics will be provided for the daily average frequency of daytime urinary incontinence episodes at baseline and week 6, together with the change from baseline (arithmetic mean and least-squares [LS] mean); the 95% confidence intervals (CI) of the arithmetic and LS mean change will be provided.

For each of the BOTOX doses of 200 U and 100 U, the null hypothesis is that there is no difference between that dose group and the 50 U BOTOX dose group in mean change from baseline in daily average frequency of daytime urinary incontinence episodes at week 6. The alternative hypothesis is that there is a difference in mean change from baseline in daily

average frequency of daytime urinary incontinence episodes between that BOTOX dose group and the 50 U dose group at week 6.

[figure not shown]
The hypotheses will be tested using an ANCOVA model with baseline value as covariate and treatment group, age (< 12 years or  $\geq$  12 years), baseline daytime urinary incontinence episodes (a total of  $\leq$  6 episodes or  $>$  6 episodes over the 2-day diary collection period), and concurrent anticholinergic therapy (use or nonuse) as factors.

A hierarchical analysis strategy (Lubsen and Kirwan, 2002) will be used to control type I error due to the multiplicity issues related to the primary efficacy analyses for the primary efficacy variable. In the order of (1) 200 U versus 50 U BOTOX, and (2) 100 U versus 50 U BOTOX, treatment group differences will be tested at the 0.05 significance level in a fixed sequence fashion. Results of hypothesis testing for 100 U versus 50 U BOTOX will be considered for statistical significance only if the treatment difference for 200 U versus 50 U BOTOX is shown to be statistically significant.

The treatment difference in mean change from baseline for 200 U versus 50 U BOTOX and 100 U versus 50 U BOTOX will be calculated, as well as the 95% CI of these differences.

The treatment-by-investigator interaction will be assessed.

### 7.3.2 Secondary Efficacy Analyses

### **7.3.2.2 Efficacy Analyses for the Secondary Efficacy Variables**

[figure not shown]
The analysis of MCC, PdetMax, and average urine volume at first morning catheterization at week 6 after treatment will generally be analyzed as described for the primary efficacy endpoint in Section 7.3.1, except that the hierachal testing strategy will not be implemented. For the urodynamic variables, only the central reviewer's interpretation will be analyzed.

[figure not shown]
For analysis of MCC, data will also be presented as a proportion of the EBC, where EBC = (30 + [age in years × 30]) for volumes below the adult volume of 500 mL (age is at the time of the assessment).

The proportions of patients with presence/absence of an IDC at week 6 will be presented and analyzed using the CMH method (200 versus 50 U BOTOX and 100 versus 50 U BOTOX) controlling for age (< 12 years or ≥ 12 years), baseline daytime urinary incontinence episodes (a total of ≤ 6 episodes or > 6 episodes over the 2-day diary collection period), and concurrent anticholinergic therapy (use or non-use).

For the analysis of night time urinary incontinence, the numbers and proportions of patients who experienced night time urinary incontinence on 0, 1, or 2 nights will be presented.

Analysis of time to patient request for retreatment and time to patient qualification for retreatment will be performed as described in Section 7.3.3.4 Duration of Effect.

AUC = area under the curve

[REDACTED]  
[REDACTED]  
[REDACTED]  
[REDACTED].

#### 7.3.3.4 Duration of Effect

A preliminary estimate of duration of treatment effect will be assessed on completion of this study (on completion of the extension study, a further estimate will be presented using data integrated across both studies). Time from treatment on day 1 to request for retreatment will be estimated using the Kaplan-Meier survival method for each treatment group. For those patients who did not request retreatment, their data will be censored using the date of their last study visit. The proportions of patients/parents/caregivers requesting retreatment during the study and the median duration by days/weeks will also be presented.

In addition, time to qualification for retreatment will be presented and analyzed as described above for time to request for retreatment.

#### 7.4 Safety Analyses

All safety analyses will be conducted on the safety population. Safety variables are adverse events, serious adverse events, [REDACTED]

[REDACTED]  
[REDACTED]  
[REDACTED]

[REDACTED]  
[REDACTED]  
[REDACTED]  
[REDACTED]

[REDACTED]  
[REDACTED]  
[REDACTED]

## 7.5 Sensitivity Analysis

Sensitivity analyses of the primary efficacy variable, using both the PP population and the median imputation method for the mITT population will be performed. Missing values will be imputed by using the median of the nonmissing values within the same treatment group at the same timepoint.

In addition, the change from baseline and responder analyses previously described using the normalized daily average frequency of daytime urinary incontinence episodes will also be conducted without the normalization of the variable to a 12-hour daytime period.

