### **7.1 Analysis Populations**

Two different populations will be defined for the statistical analysis: safety and modified intent-to-treat (mITT).

The safety population will include all patients who undergo the treatment procedure and receive study drug on randomization/day 1 and will be analyzed on an as-treated basis

(ie, using the dose actually received with all patients allocated to the nearest dose group [50, 100, or 200 U BOTOX]).

The mITT population will include all randomized patients who received treatment on randomization/day 1 and will be analyzed on an as-randomized basis, except for patients who received less than their randomized dose due to the limit of 6 U/kg, as they will be grouped to the nearest dose group (50, 100, or 200 U BOTOX) based on the dose actually received. Demographics, baseline characteristics, and efficacy variables will be analyzed using the mITT population.

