## 7.7 Sample Size Calculation

The sample size calculation for this study is determined empirically, while taking into account the treatment effect observed in the adult pivotal phase 3 studies, 191622-515 and 191622-516. The mean (standard deviation) of the change from baseline in daily urinary incontinence at week 6 was -3.1 (3.44) and -3.1 (2.58) in Studies 191622-515 and 191622-516, respectively.

Approximately 34 patients per treatment group are to be enrolled for the study. This includes 30 patients per treatment group and an increase to 34 per group in order to address patient attrition (estimated to be 10% by week 6)

The following table displays estimates of the distance for treatment differences between BOTOX 200 U (maximum 6 U/kg) and 50 U (maximum 6 U/kg) in mean daily average frequency of daytime episodes of urinary incontinence change from baseline at week 6 for a range of common standard deviations (SD). All calculations assume 30 patients per treatment group and a 2-sided test significance level of 0.05. The calculation was performed using the commercial software nQuery Advisor (procedure MTC0-1), version 6.01, and the CI is based on the large sample z statistic.

Standard Deviation	Distance From Mean to the Limit
2.0	1.012
2.5	1.265
3.0	1.518
3.5	1.771
4.0	2.024

Note: The ranges of the SDs are determined based on the values from the adult pivotal phase 3 studies (191622-515 and 191622-516). The estimate of the SD for the 200 U BOTOX treatment group is 3.44 for Study 191622-515, 2.58 for Study 191622-516, and 3.10 for the 2 studies combined.

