### Amendment Summary

Following is a summary of content-oriented changes that were made to each section of the protocol, and a brief rationale for these changes. Minor editorial and document formatting revisions have not been summarized.

Sections	Revision	Rationale
Synopsis Section 4.4: Number of Patients Section 7.7: Sample Size Calculation	Decreased the sample size from N=132 to N=102	Due to enrollment challenges, the sample size was recalculated. While the revised sample size will provide a wider confidence interval than the current sample size, the proposed reduction should not negatively affect the clinical and scientific integrity of the study. The FDA has concurred with this plan.
Section 7.1: Analysis Populations	Deleted Per-protocol population	To reflect current company standard for not performing analyses on per-protocol population for superiority trials.

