5.2 Primary Efficacy Analyses

5.2.1 Primary Analyses of Primary Efficacy Variable

For each of the BOTOX doses of 200 U and 100 U, the null hypothesis is that there is no difference between that dose group and the 50 U BOTOX dose group in mean change from baseline in daily average frequency of daytime urinary incontinence episodes at week 6. The alternative hypothesis is that there is a difference in mean change from baseline in daily average frequency of daytime urinary incontinence episodes between the higher BOTOX dose group under consideration and the 50 U dose group at week 6.

The hypotheses will be tested using an ANCOVA model with baseline value as covariate and treatment group, age (< 12 years or \geq 12 years), baseline daytime urinary incontinence episodes (a total of \leq 6 episodes or $>$ 6 episodes over the 2-day diary collection period), and use of anticholinergic therapy (no/yes) at baseline (on day of injection) as factors.

Furthermore, the last observation carried forward (LOCF) method of imputation will be used to impute missing week 6 assessments. The fitted model will be used to derive the adjusted mean treatment differences in the primary variable (least-squares [LS] mean difference) and

[figure not shown]
associated 95% CI, for the comparison of the 50 U BOTOX treatment group versus the 200 U and 100 U BOTOX treatment groups.

After fitting the ANCOVA model, to adjust for multiplicity, a hierarchical analysis testing strategy (Lubsen and Kirwan, 2002) will be applied. Initially the 200 U versus 50 U BOTOX mITT treatment group will be tested at a two sided significance level of 5%. If it is concluded that the 200 U BOTOX treatment group has a greater mean reduction in daily average frequency of daytime urinary incontinence episodes, the 100 U versus 50 U BOTOX treatment group will be tested. In other words, results of hypothesis testing for 100 U versus 50 U BOTOX will only be considered for statistical significance if the treatment difference for 200 U versus 50 U BOTOX is shown to be statistically significant.

Furthermore, the average daytime duration will be summarized for each visit.

Apart from the hierarchical testing, the analysis outlined above will also be repeated for the week 2, and 12 visit diary assessments. No imputation method will be applied in these analyses.

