6.2 Adverse Events

[figure not shown]
Adverse events (AEs) will be coded by system organ class and preferred term using the Medical Dictionary for Regulatory Activities (MedDRA).

[figure not shown]
Pre-treatment AEs are AEs that have start date on or after the signing of consent form and prior to the BOTOX injection.

[figure not shown]
An AE will be considered a treatment-emergent adverse event (TEAE) if it was present after the first dose of study treatment or was present before the date of the first dose of study treatment and increased in severity or became serious after the first dose of study treatment.

[figure not shown]
The number and percentage of patients reporting TEAE in each treatment group will be tabulated by descending percentage in any group, by system organ class and preferred term, and further categorized by severity and causal relationship to the study drug and study drug injection procedure. If more than 1 AE is coded to the same patient, the patient will be

[figure not shown]
counted only once for that preferred term using the greatest severity for the summarization by severity and causal relationship.

[figure not shown]

[figure not shown]
[figure not shown]

[figure not shown]

9. Interim Analyses

No interim analysis is planned for this study. However, there is a Data Review Committee (DRC) that reviews, on regular bases, selected blinded safety analyses. There is a separate DRC charter and analysis plan that outlines the function of the DRC and what they will be reviewing.

10. Analysis for US FDA

Not applicable.

11. Data Collected but not Analyzed

A patient's surgical history and female patients' birth control treatment during the study are collected in this study. No output will be generated for these data.

12. Deviations from Protocol

There are no deviations from the protocol.

13. References

Mallinckrodt CH, Clark WS, David SR (2001a). Type I error rates from mixed-effects model repeated measures versus fixed effects analysis of variance with missing values imputed via last observation carried forward. *Drug Information J*. 2001a;35:1215-1225.

Mallinckrodt CH, Clark WS, David, S. R. (2001b). Accounting for dropout bias using mixed-effects models. *J. Biopharmaceutical Statistics*. 2001b;11:9-21.

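### Protocol 7.5 fills missing values with the arm median: at the planned 10% attrition the CI is about 10% too narrow and the nominal 5% test runs at about 6–8%

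*Protocol*

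**What the plan says.** The primary variable is the change from baseline at week 6 in daily daytime incontinence episodes, analysed by ANCOVA in the mITT population. Protocol 7.2.1 states that, up to week 6, "missing frequencies of episodes of daytime urinary incontinence will be replaced using the last observation carried forward approach". SAP 5.2.1 agrees: "the last observation carried forward (LOCF) method of imputation will be used to impute missing week 6 assessments".

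Protocol 7.5 then promises sensitivity analyses of the primary variable "using both the PP population and the median imputation method for the mITT population will be performed", and defines the second of these: "Missing values will be imputed by using the median of the nonmissing values within the same treatment group at the same timepoint". Its only other item repeats the analyses without the 12-hour normalization.

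Protocol 7.1 now defines only the safety and mITT populations, and the Amendment 3 summary records "Deleted Per-protocol population". SAP Amendment 1 likewise removed every per-protocol analysis. The visible SAP has no section on missing-data sensitivity, and its section 12 says "There are no deviations from the protocol".

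Protocol 7.7 plans 34 patients per arm, so that 30 remain after an estimated 10% attrition by week 6.

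**The concern.** With the per-protocol analysis gone, and the un-normalized rerun addressing a different question, median imputation is the only check on LOCF in the visible text. It is a poor one. All missing patients in an arm receive one identical value, which the ANCOVA treats as real data. The filled values add almost nothing to the residual sum of squares but add fully to the degrees of freedom and the sample size, so the standard error is understated.

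No confirmatory decision depends on this analysis. What is at stake is how the primary result is read. The point estimate may move away from the LOCF estimate, which is informative. The interval around it, however, would be narrower than the LOCF interval, and narrower even than if nobody were missing. A check on missing data should not gain precision from the missing data.

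**Working it through.** **Inputs.** From Protocol 7.7: N = 34 per arm, 10% attrition by week 6, two-sided 0.05, z-based interval, SD 2.0 to 4.0. From Protocol 7.3.1: ANCOVA with the baseline value and factors for treatment, age, baseline episodes and anticholinergic use. From Protocol 7.5: the imputation rule.

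**1. The plan's own figures.** Half-width = 1.96 × SD × √(2/n). With n = 30 and SD 2.0, 2.5, 3.0, 3.5 and 4.0 this gives 1.012, 1.265, 1.518, 1.771 and 2.024, matching the table in 7.7. Also 30/0.9 rounds up to 34.

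**2. Closed form for median filling.** Let n of N patients per arm be observed. If the median lies close to the mean, the residual sum of squares hardly changes, so the estimated variance shrinks by (n−1)/(N−1). The standard error then uses N in place of n. Hence

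reported SE / valid SE ≈ √[(n−1)/(N−1)] × √(n/N), and actual alpha ≈ 2 × [1 − Φ(1.96 × ratio)].

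At 10% missing, n = 30.6 and SD 3.0:
- observed patients only: 1.96 × 3 × √(2/30.6) = 1.503
- complete data on 34: 1.96 × 3 × √(2/34) = 1.426
- median-filled: 1.426 × √(29.6/33) = 1.351
- ratio: 1.351/1.503 = 0.899; actual alpha 7.8%

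For whole patients per arm, the ratio and alpha are 0.940 and 6.5% (2 of 34 missing), 0.910 and 7.4% (3 missing), and 0.881 and 8.4% (4 missing, which leaves 30). SD cancels from the ratio.

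**3. Simulation of the planned ANCOVA.** Three arms of 34, 200 U versus 50 U, no true difference, data missing completely at random, 12,000 trials per cell (Monte Carlo error about 0.2 points). Type I error of the median-filled test:

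| Missing at week 6 | Near-normal | Overdispersed 2-day counts | Lognormal |
|---|---|---|---|
| 3% | 5.8% | 5.0% | 5.1% |
| 5% | 6.3% | 5.4% | 5.3% |
| 10% | 7.7% | 6.2% | 6.1% |
| 15% | 9.9% | 7.4% | 6.8% |

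At 10% missing, the observed-case test held 4.5–4.9%, and reported SE over true SE for median filling was 0.89 (near-normal) and 0.92 (both skewed cases). Mean half-widths at 10%:

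| Outcome | Median | LOCF | Complete | Observed |
|---|---|---|---|---|
| Near-normal | 1.288 | 1.340 | 1.346 | 1.426 |
| Counts | 0.927 | 0.972 | 0.974 | 1.028 |
| Lognormal | 1.064 | 1.109 | 1.113 | 1.176 |

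Median filling is about 10% narrower than observed cases (1.288/1.426 = 0.903) and 4–5% narrower than either LOCF or complete data.

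**4. Variations.**
- A separate ANCOVA simulation with fixed numbers missing (4,000 runs per scenario, Monte Carlo error about 0.4 points) gave 7.1–8.4% (normal) and 5.8–6.6% (skewed) with 3 of 34 missing, and 7.7–9.6% and 5.9–7.3% with 4 missing.
- If the median is taken of the change rather than the frequency and the data are skewed, the interval is 2–5% wider than observed cases. It is still 5–11% too narrow for its own sampling variation.
- If missingness depends on the week 2 value equally in all arms, median filling gives 7.9% (near-normal) and 6.3% (counts).

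**5. The alternative.** Multiple imputation using week 2 (10 imputations, 6,000 trials) gave 5.2%, 4.9% and 4.4% in the three outcome cases at 10% missing. Its half-widths were 1.42, 1.04 and 1.18, against 1.29, 0.93 and 1.07 for median filling in the same runs. With missingness dependent on week 2 it gave 4.8% (near-normal) and 4.5% (counts).

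**The case against.** The strongest objection is that a better check may exist out of sight. The SAP's reference list includes two methodological papers on mixed-effects repeated-measures models, one of them comparing such models with LOCF, and nothing in the visible text cites either. SAP 2.3.1 ties LOCF to the primary analysis, which hints at another method elsewhere, and parts of the efficacy section are blacked out. An MMRM may well be in the plan. That stands: it limits any claim that no other check exists. It does not rescue Protocol 7.5, which prescribes median filling in open text. Following it prints an interval that is too narrow whatever else is run.

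A second objection is that readers will set this analysis beside LOCF, where the widths differ by only 4–5%, and not beside an observed-case analysis. The width comparison is fair. But in a further simulation of the planned ANCOVA at 10% missing, LOCF held 4.5–5.0% and observed cases 4.8–5.0%, while median filling gave 6.5–7.4%. The excess error is therefore not shared by the analysis being checked.

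A third is that the upper end of 6–8% comes from near-normal data, whereas the endpoint is a diary count. That is partly right: one count model gave 6.2%, but another, in that further simulation, gave 7.4%.

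Fourth, 10% is planned dropout, not the rate of missing week 6 diaries, and one valid diary day is enough for a value. This stands, and the effect fades as missingness falls.

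Fifth, mITT regroups patients affected by the weight cap. A patient randomized to 200 U and weighing under 25 kg (6 × 25 = 150 U) is analysed in a lower dose group, so the arms will not all be 34. The absolute half-widths are illustrative; the ratios hold.

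**Conclusion.** The concern holds. At 10% missing, the median-filled analysis reports a standard error roughly 0.89–0.94 of the true one, and its nominal 5% test rejects in about 6–8% of null trials. With 4 of 34 missing per arm and near-normal data it can go higher. At 3% missing the problem is negligible.

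These figures assume that the attrition falls after injection, and so within mITT; that data are missing completely at random, apart from the week 2 variant; and, in the main simulation, a week 2–week 6 correlation of 0.6 (on the latent scale for skewed outcomes) and a chosen degree of skew. The documents give none of these. Bias from using a median in skewed data when a real effect exists was not simulated.

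The defect lies in a supportive analysis. The LOCF ANCOVA and its fixed-sequence testing are untouched. It should be corrected, but it does not threaten the confirmatory result.

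**What to change.** Replace the first paragraph of Protocol 7.5 with:

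> A sensitivity analysis of the primary efficacy variable will be performed on the mITT population. Missing week 6 values will be multiply imputed from a regression on treatment group, baseline value, age stratum, baseline-episode stratum, anticholinergic use and the week 2 value, analyzed with the primary ANCOVA and combined by Rubin's rules.

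An MMRM on weeks 2, 6 and 12 with the same factors is an acceptable alternative. Report the result beside the LOCF primary and keep the un-normalized rerun. The new wording also removes the leftover per-protocol reference.

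Check the SAP's redacted sections. If they already contain such an analysis, bring the protocol into line with it; if not, add it. The SAP should also fix the number of imputations, the seed and the handling of negative imputed frequencies. Both options assume missingness at random, so departures from that would remain untested.

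The cost is one protocol paragraph, a matching SAP check and modest programming, with no new data. The sensitivity interval becomes about 10–12% wider than under median filling (1.42/1.29 = 1.10; 1.04/0.93 = 1.12; 1.18/1.07 = 1.10), which reflects the information actually collected.
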